## **ICARE PROTOCOL AND ANALYSIS PLAN**

**Study Title: A New Approach to Vision Therapy Based on Naturalistic 3-D Computer Gaming**

**Study ID: ICARE2B**

**Document Date: 8/30/2023**

**NCT number: NCT03066063**

The research team will execute two concurrent studies within a common framework. The first will compare iCare to standard of care occlusion therapy (patching) for amblyopia in patients ages 4 to 18 (inclusive). The second will compare iCare to a standard of care for home-based CI therapy (pencil pushups) for convergence insufficiency patients ages 8 to 18 (inclusive). In the context of this study, the term iCare refers to either the amblyopia or CI video game module as appropriate for the respective study group.

Both the amblyopia and CI studies will follow the same basic approach. Each study will last 12 weeks, and participants will return for follow-up visits at Weeks 4, 8, and 12. Patients will receive full visual exams to establish baseline data upon enrollment, and again at Week 12 to record post-treatment data. During the interim visits (Weeks 4 and 8), patients' visual function will be assessed by a study optometrist, and any changes to the iCare configuration will be addressed as needed. As iCare is a home-based therapy, participants must have access to a personal computer and the Internet. For patients without access, the research team will provide loaner computers and/or pre-paid Verizon wireless mobile hotspots for Internet connectivity.

The proposed clinical studies will use the provider-as-investigator model that involves a minimum of 10 study sites and approximately 100 participants (see statistical power analysis below). With this approach, the research team will recruit optometry and vision therapy clinics and practices from around the country to support study execution under the training, guidance, and supervision of the iCare team. UND will serve as the "coordinating center" [48], enrolling, training, and overseeing the study sites and providing Institutional Review Board (IRB) governance. The UND team has experience in successfully serving in this multi-center coordination role in related research (see Biosketches). Enrolled providers (known hereafter as *investigator-providers*) will, in turn, recruit participants from their own patient rosters. This model serves several important purposes:

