### **Amblyopia study**

Children (ages 4-18) with amblyopia and meeting study inclusion/exclusion criteria will be recruited according to IRB-approved procedures. Informed consent will be sought from the parents or legal guardian with assent from the child. Enrollees will be randomized to one of two groups. A standard of care group will be prescribed patching for two or six hours per day, seven days per week. Standard of care group participants with best-corrected vision worse than 20/200 in their amblyopic eye will be prescribed six hours of patching daily, while participants whose best-corrected visual acuity is 20/200 or better will be prescribed two hours of patching daily. Participants assigned to an experimental group will play iCare vision therapy games for approximately 20 minutes per day, five days per week. Assignments will be made via a block randomization scheme based on a random permutation. With regards to age, it is expected that amblyopia patients between ages 4 to 6 years may experience up to one line (0.1 logMAR) greater improvement than those over 6 years of age [51]. For this reason, assignments within the amblyopia patient cohort will be age-balanced.

The primary investigational hypothesis is that the improvement in best-corrected visual acuity for participants in the iCare experimental group will not be inferior to the level of improvement observed in the standard of care (patching) group. An ETDRS (Early Treatment Diabetic Retinopathy Study) logMAR (logarithm of the minimum angle of resolution) chart [52] will be used as the primary assessment of visual acuity (VA). To reduce test-retest-variability, scoring will be based on an interpolated logMAR value (single-letter score) based on all measurements via the formula,  $VA = 1.1 - T_c L_v$ , where  $T_c$  is the total number of correctly read letters and  $L_v$  is the logMAR value of each letter on the chart (0.02 for ETDRS) [53]. In children 4-6 years old, a Lea Symbols chart [46] will also be used, with the best VA score from the two tests used for primary analyses.

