Secondary analyses will test, on a per intervention basis, the null hypotheses that the mean  $\Delta$  logMAR for each treatment group mean (iCare and patching) is greater than or equal to zero, with the alternative hypothesis that the mean  $\Delta$  logMAR of the respective study-population is less than zero (indicating improved acuity associated with the respective treatment between pre-/post-testing). Additionally, systematic relationships between  $\Delta$  logMAR and age, gender and per-intervention logMAR will be examined in secondary factorial analysis.

Statistical power analysis for the amblyopia study is based on selecting N such that there is at least an 80% probability of rejecting the primary null hypothesis (when the alternative hypothesis is true) that the mean  $\Delta$  logMAR of the iCare experimental study population minus the mean  $\Delta$  logMAR of the patching experimental study population exceeds the non-inferior threshold. Assuming a standard deviation in acuity improvement between subjects of approximately 2 lines on the ETDRS chart (0.2 logMAR – consistent with observed variability in previous studies [51], [26]), at least 50 patients must complete the amblyopia study (25 each in the iCare and patching groups) to achieve adequate statistical power. Thus, if the true mean of the  $\Delta$  logMAR distribution for the iCare group is less than or equal to (better than) the true mean of the  $\Delta$  logMAR distribution for the patching group, there is an 80% chance that the null hypothesis of iCare amblyopia therapy inferiority to patching amblyopia therapy will be correctly rejected. To account for potential dropouts, up to 64 total patients will be consented into the amblyopia study.

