The primary null hypothesis will be that the mean of the  $\Delta$ BOB distribution is the same for the iCare and control groups, with the alternative hypothesis that the mean  $\Delta$ BOB is greater (i.e. indicating greater improvement) for the iCare group. A one-sided  $p \leq 0.025$  decision rule will be utilized to test the null hypothesis. Secondary null hypotheses will test, on a per intervention basis, whether the mean  $\Delta$ BOB of the study-population is equal to zero, with the alternative that the respective study-population  $\Delta$ BOB is greater (indicating improved functional vergence). Additionally, relationships between  $\Delta$ BOB and age, gender, and pre-intervention BOB will be systematically examined employing the LMM. NPC data will be analyzed in an identical manner.

Statistical power analysis for the CI study is based on selecting N such that there is at least an 80% probability of rejecting the primary null hypothesis when the alternative hypothesis is true. With N=50 (25 patients per group) the underlying minimum detectable difference in the mean positive fusional vergence in convergence is 7.3 prism diopters (conservatively assuming a standard deviation of 9 prism diopters [32]). In a previous randomized controlled trial, office-based CI vision therapy was found to produce a mean difference in improvement after 12 weeks of greater than 10 prism diopters [32]. The Phase IIB CI study is therefore sufficiently powered. To account for potential dropouts, up to 64 total patients will be consented into the CI study.

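### The per-arm tests of 12-week change against zero cannot attribute a gain to the treatment, because both arms are active and no untreated reference is described

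*Combined protocol and SAP*

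**What the plan says.** In the Amblyopia study section, "Enrollees will be randomized to one of two groups". The control arm is active: "A standard of care group will be prescribed patching for two or six hours per day, seven days per week". So is the other arm: "Participants assigned to an experimental group will play iCare vision therapy games for approximately 20 minutes per day, five days per week". The primary analysis is a randomized non-inferiority comparison of the two.

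The secondary analyses are a different kind of test: "Secondary analyses will test, on a per intervention basis, the null hypotheses that the mean" change is zero or worse, against the alternative that it is below zero. The plan glosses that alternative as "indicating improved acuity associated with the respective treatment between pre-/post-testing". No alpha is given for these tests, and no caveat is attached to their reading.

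The Convergence insufficiency study section plans the same per-arm tests for BOB, with the alternative that the mean change "is greater (indicating improved functional vergence"), and says that NPC will be handled identically. Both arms there are active as well (iCare and pencil pushups).

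On timing, the overview states: "Each study will last 12 weeks, and participants will return for follow-up visits at Weeks 4, 8, and 12". It also states: "Patients will receive full visual exams to establish baseline data upon enrollment, and again at Week 12 to record post-treatment data". No stabilization or run-in period is described for either study.

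**The concern.** A test of mean change against zero shows that treatment worked only if zero is the change expected without treatment. Nothing in either design estimates that change, and there are reasons to doubt that it is zero. Participants are children, from age 4 in the amblyopia study and age 8 in the CI study, who are examined again after 12 weeks with visits in between. Familiarity with the task and maturation can both move the mean towards improvement in each arm. Regression to the mean and a change of optical correction could do the same.

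The stakes are in what may be concluded. The amblyopia primary result, if positive, says that iCare is not worse than patching by more than 0.1 logMAR. The per-arm test is the only planned analysis that bears on whether iCare itself improves acuity, and it cannot answer that question. In the CI study, a significant per-arm gain could stand beside a primary superiority test that fails, and a reader would need to know that the former is not evidence of a treatment effect.

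**Working it through.** **The plan's own figures.** The plan gives no operating characteristics for the per-arm tests, so there is no figure to reproduce for them. The inputs come from its two power statements.

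- Amblyopia: SD of change 0.2 logMAR, 25 completers per arm.
- CI: SD 9 prism diopters (PD), 25 per arm. With these inputs the stated minimum detectable difference of 7.3 PD reproduces (7.28 by noncentral t, two-sided 0.05, 80% power).
- Alpha: the CI primary test uses one-sided 0.025. No level is stated for the per-arm tests, so 0.025 is used here, with 0.05 beside it for amblyopia.

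The plan's 25 per arm for the amblyopia primary test does not follow from SD 0.2 and a 0.1 margin at 80% power (63 per arm at one-sided 0.025, 50 at 0.05). That is a separate matter. Here 25 is simply the planned arm size.

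**Step 1: the gain an arm needs to be declared improved.** Standard error = SD/√n.

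- Amblyopia: 0.2/√25 = 0.04 logMAR. With 24 degrees of freedom the critical t is 2.064 at one-sided 0.025 and 1.711 at 0.05. The observed mean gain must exceed 2.064 × 0.04 = 0.083 logMAR, or 1.711 × 0.04 = 0.068. At 0.02 logMAR per letter, 0.083 is about four letters.
- CI: 9/√25 = 1.8 PD, so the threshold at 0.025 is 2.064 × 1.8 = 3.7 PD.

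The test does not use the cause of the gain.

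**Step 2: how often an arm with no treatment effect crosses that threshold.** Suppose the treatment does nothing and the mean shifts by d for other reasons. The rejection probability is that of a noncentral t with 24 degrees of freedom and noncentrality d/SE. Every d below is an assumption; the documents give no non-treatment change.

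| Assumed shift | d/SE | One-sided 0.025 | One-sided 0.05 |
|---|---|---|---|
| 0.02 logMAR | 0.50 | 7% | 12% |
| 0.05 logMAR | 1.25 | 22% | 33% |
| 0.075 logMAR | 1.875 | 44% | 57% |
| 0.10 logMAR | 2.50 | 67% | 78% |
| 2 PD | 1.11 | 19% | not computed |
| 3 PD | 1.67 | 36% | not computed |
| 5 PD | 2.78 | 76% | not computed |

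If all 64 consented amblyopia patients completed (32 per arm), the 0.10 logMAR row would rise to 78% at one-sided 0.025.

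**Step 3: the randomized contrast.** If both arms share a shift d, the expected difference is (iCare effect + d) − (control effect + d) = iCare effect − control effect. The shift cancels in the primary analyses and stays in full in each per-arm test.

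**The case against.** The strongest reply is that this is a labelling point on secondary tests. The gloss speaks of association, not causation, and the CI wording names no treatment at all: it merely describes a mean change above zero. Both primary inferences are randomized contrasts, in which shared change cancels. If the true mean change is −0.05 logMAR for whatever reason, the stated null is false and rejecting it is correct, so type I error is not inflated. A 95% confidence interval that excludes zero also carries the same information as the one-sided 0.025 test.

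Most of this stands, and it limits the point. What it does not remove is that the amblyopia gloss ties the gain to the respective treatment, without a caveat, in a design that has no reference for change without treatment. An interval labelled as descriptive keeps the information and drops that reading.

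Stronger readings are tempting but unsupported:

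- *Any mean gain counts as improvement.* It does not; at 25 per arm the observed gain must exceed about 0.083 logMAR at one-sided 0.025.
- *An inactive therapy would come out positive.* It could. At one-sided 0.025 the probability passes one half only for the largest shift assumed in each study.
- *Regression to the mean, updated correction and retesting on the same charts at Weeks 4 and 8 are established.* They are not. The entry criteria are not listed, acuity is best-corrected, and the tests used at interim visits are not named.
- *The fellow eye could serve as an untreated comparator.* It is doubtful. It is not the eye with the deficit, it may have less room to improve, patching may affect it, and its Week 12 acuity is only inferred from the full exam.

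**Conclusion.** The point holds as one of interpretation. A significant per-arm gain in the amblyopia study would not support the reading that the plan attaches to it. The per-arm BOB and NPC tests have the same design limit, with milder wording. Neither primary comparison is biased by change common to both arms.

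The size depends on a quantity that the documents do not give. Across assumed shifts of 0.05 to 0.1 logMAR, an arm with no treatment effect is declared improved in 22% to 67% of trials at one-sided 0.025 (33% to 78% at 0.05). Across 2 to 5 PD the range is 19% to 76% at 0.025. These figures rest on 25 completers per arm, SDs of 0.2 logMAR and 9 PD, and a one-sample t-test in place of any model-based equivalent. They show how readily non-treatment change could be read as benefit; they do not show that the tests exceed their nominal level against the stated null.

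Practice and maturation are the alternatives that the design makes directly plausible, through children's ages and repeat visits. The others remain possibilities.

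**What to change.** In the secondary analyses of both the Amblyopia study and the Convergence insufficiency study sections:

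1. Replace the per-arm hypothesis tests (logMAR, BOB, NPC) with each arm's mean 12-week change and 95% confidence interval, labelled as descriptive.
2. In the amblyopia section, delete the words that tie improved acuity to the respective treatment.
3. State that only the randomized iCare-minus-control contrast supports a conclusion about treatment, and that in the amblyopia study this contrast can show non-inferiority to patching, not benefit over no treatment.

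This is a change of wording in the analysis plan. It needs no extra visits, patients or measurements. The small cost is that the sponsor gives up per-arm p-values that might have been favourable; the estimates themselves are kept.

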The pre- to post-intervention change in best-corrected vision ( $\Delta$  logMAR) at 12 weeks will serve as the primary efficacy endpoint. In terms of hypothesis testing, the primary null hypothesis will correspond to a non-inferiority test in which the null hypothesis will be that the mean of the  $\Delta$  logMAR distribution for the iCare experimental study population is greater than that of the patching experimental study population (indicating inferior average outcome), while the alternative hypothesis will be that the mean  $\Delta$  logMAR for the iCare experimental study population is equal to or more negative than the mean  $\Delta$  logMAR patching experimental study population (indicating iCare therapy is non-inferior to patching therapy with respect to improving visual acuity). The null hypothesis will be rejected if the upper 95% confidence limit for the between-group difference (i.e. iCare – patching) in mean  $\Delta$  logMAR does not exceed the non-inferior threshold of one line on an ETDRS chart (approximately 0.1 logMAR). Analysis will be performed by way of a linear mixed model (LMM) in which the pre- to post-intervention change ( $\Delta$  logMAR) will be the LMM dependent variable, while the intervention (iCare vs. patching) will serve as the primary LMM independent variable and patient age, gender, pre-intervention logMAR in the amblyopic eye, and logMAR in the fellow eye will all serve as secondary LMM independent variables. These secondary variables will be utilized to adjust for any between-intervention disparities in age, gender, pre-intervention logMAR in the amblyopic eye, and logMAR in the fellow eye. Inclusion of these secondary independent variables in LMM will also allow assessment of the impacts on these characteristics on outcomes. Additionally, a stratification variable “study site” will be incorporated into the LMM as a random-effect to account for within study-site measurement correlation as well as between study-site variability.

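### On the plan's own inputs, 25 completers per group give the amblyopia non-inferiority test about 41–55% power, not 80%; the factor of 2 for comparing two groups appears to have been left out.

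*Combined protocol and SAP*

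**What the plan says.** All of the following is in the Amblyopia study section of the combined protocol and SAP unless noted.

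- **Decision rule.** "The null hypothesis will be rejected if the upper 95% confidence limit for the between-group difference" in mean change in logMAR (iCare minus patching) "does not exceed the non-inferior threshold of one line on an ETDRS chart (approximately 0.1 logMAR"). The plan does not say whether this limit is one-sided or the upper end of a two-sided interval.
- **Power target.** The number of patients is chosen so that "there is at least an 80% probability of rejecting the primary null hypothesis (when the alternative hypothesis is true").
- **Variability.** "Assuming a standard deviation in acuity improvement between subjects of approximately 2 lines on the ETDRS chart (0.2 logMAR").
- **True difference.** The power is claimed whenever the iCare mean change "is less than or equal to (better than) the true mean of the" patching distribution, which includes exact equality.
- **Result.** "at least 50 patients must complete the amblyopia study (25 each in the iCare and patching groups) to achieve adequate statistical power", and hence "there is an 80% chance that the null hypothesis of iCare amblyopia therapy inferiority to patching amblyopia therapy will be correctly rejected". Up to 64 patients may be consented to cover dropouts.

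The Convergence insufficiency study section makes a parallel calculation for the sister study with the same group size: "With N=50 (25 patients per group) the underlying minimum detectable difference in the mean positive fusional vergence in convergence is 7.3 prism diopters", for a standard deviation of 9 and a one-sided 0.025 test.

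**The concern.** The two power statements do not sit together. With 25 per group and 80% power, the convergence insufficiency study is said to detect 7.3/9 = 0.81 standard deviations. With the same group size and power, the amblyopia study is said to exclude a margin of 0.1/0.2 = 0.5 standard deviations. At a common significance level both cannot be true, and the plan states no level for the amblyopia calculation that could explain the gap.

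This is the primary hypothesis of the amblyopia study. If the 80% is wrong, anyone relying on the plan expects a one-in-five risk of missing non-inferiority when the treatments are equal, while the real risk is around one in two. A non-significant result could then be taken as evidence against iCare when it mostly reflects imprecision.

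**Working it through.** **Inputs** (Amblyopia study section): standard deviation 0.2, margin 0.1, true difference 0, 25 per group, target power 80%. Because the meaning of the upper 95% limit is open, both one-sided 0.05 and one-sided 0.025 are used.

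**1. Reproducing the plan's 25.** The formula without a factor of 2 (one-sample form) is n = (SD/margin)² × (z_α + z_β)².

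- One-sided 0.05: (0.2/0.1)² × (1.645 + 0.842)² = 24.7, rounded up to 25. This matches the plan.
- One-sided 0.025: 31.4, so 32. This does not match.

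**2. Two independent groups.** The formula is n per group = 2 × (SD/margin)² × (z_α + z_β)².

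- One-sided 0.05: 49.5, so 50 per group (51 by noncentral t).
- One-sided 0.025: 62.8, so 63 per group (64 by noncentral t).

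At one-sided 0.05 the right answer per group is 50, which is the number the plan uses as its total. Even at one-sided 0.10, 37 per group would be needed, and 25 per group would give only about 68%.

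**3. Power with 25 per group.** SE = 0.2 × √(2/25) = 0.0566, and margin/SE = 0.1/0.0566 = 1.768.

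| Reading of the upper 95% limit | Normal approximation | Noncentral t, 48 df |
|---|---|---|
| One-sided 95% (α = 0.05) | Φ(1.768 − 1.645) = 54.9% | 53.9% |
| Upper end of two-sided 95% (α = 0.025) | Φ(1.768 − 1.960) = 42.4% | 41.0% |

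Under the second reading the half-width of the interval at SD 0.2 is 0.114, larger than the margin. An observed difference of exactly zero would therefore fail.

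**4. If all 64 consented patients were analysed** (32 per group), t-based power is 63.1% (α = 0.05) or 50.4% (α = 0.025).

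**5. What would give 80% at 25 per group** (t-based, α = 0.05 or 0.025):

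- a margin of 0.143 or 0.162 logMAR; or
- a residual SD of 0.2 × 0.1/0.143 = 0.140, or 0.2 × 0.1/0.162 = 0.124. Covariates would then have to explain 1 − (0.140/0.2)² = 51%, or 1 − (0.124/0.2)² = 62%, of the variance.

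A true iCare advantage of about 0.041 or 0.058 logMAR (normal approximation) would also do it, but the plan claims 80% at equality.

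**6. Check against the convergence insufficiency study.** A two-sample noncentral-t calculation with 25 per group, SD 9 and one-sided 0.025 gives a detectable difference of 7.28, which reproduces the stated 7.3. At one-sided 0.05 it would be 6.42, or 0.71 standard deviations, still well above 0.5. The sister study's calculation therefore uses a proper two-group formula and the amblyopia calculation does not agree with it.

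**The case against.** **The cause is inferred.** The plan shows no formula and no significance level for this calculation. The missing factor of 2 reproduces 25 only at one-sided 0.05, and other origins are possible, such as carrying over the sister study's N of 50. This stands: the cause is likely, not proven. The shortfall does not depend on it, because no conventional level gives 80%. In the same way, the convergence insufficiency figure shows an inconsistency but does not prove the mechanism.

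**The planned analysis is not a t-test.** The mixed model adjusts for age, gender, baseline acuity in the amblyopic eye and acuity in the fellow eye, with site as a random effect. Adjusted power could exceed 41–55%, so these figures describe an analysis whose residual SD is the stated 0.2. That qualification stands, but it does not rescue the claim. The power paragraph takes no credit for adjustment, and covariates would have to explain 51–62% of the variance. The one covariate effect the plan quantifies, up to 0.1 logMAR between younger and older children, would explain at most 0.25 × 0.1²/0.2² = 6% when treated as two equal age bands.

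**The inputs are approximate.** Both the margin and the SD are described as approximate. Moving both favourably, to 0.11 and 0.19, still gives only about 65% at one-sided 0.05.

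**Interpretation of a failed test.** The plan does not say how a non-rejection would be read, so the risk of misreading is a reasonable worry and not something the plan commits to.

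**Conclusion.** The stated 80% is wrong under either reading of the upper 95% limit. With SD 0.2, margin 0.1, equal true means, 25 completers per group and no variance reduction from covariates, power is about 54% (one-sided 0.05) or 41% (one-sided 0.025). The range 41–55% also covers the normal approximation. For 80% the study needs about 102 or 128 completers in total (51 or 64 per group), roughly two to two and a half times the 50 planned. Full retention of all 64 consented patients would not close the gap. Omission of the two-group factor of 2 is the most likely explanation.

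**What to change.** Revise the power paragraph of the Amblyopia study section:

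1. State whether the upper 95% limit is one-sided 95% or the upper end of a two-sided 95% interval. The corrected figures depend on this.
2. Withdraw the statements that 50 completers are adequate and that power is 80%. Possible replacement: *With 25 completers per group, a standard deviation of 0.2 logMAR, a margin of 0.1 logMAR and no true difference, power is about 54% (one-sided 0.05) [or 41% (one-sided 0.025)]. Power of 80% would require about 51 [or 64] completers per group.*
3. If covariate adjustment is expected to supply the missing power, state the residual SD assumed (at most 0.140 or 0.124) and the evidence for it.
4. Add that failure to reject will be reported as inconclusive, together with the confidence interval. This is good practice and separate from the arithmetic.

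The cost of these changes is wording only. Enrolment need not change, but the stated power becomes less favourable and the trial remains underpowered. The sponsor should say openly whether it accepts that, justifies a smaller residual SD, or enlarges the study. At the dropout allowance implied by 64 consented for 50 completers, 80% power would mean consenting about 102 × 64/50 ≈ 131 or 128 × 64/50 ≈ 164 patients, against the current ceiling of 64.
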